8.6 Early Termination and Withdrawal

All subjects are free to withdraw from participation in the study at any time upon request via letter as described on the consent form.

The Principal Investigator (PI) may discontinue or withdraw a healthcare worker from the study at her discretion for failure to consider use of the integrated care model with their patient participants, although deviation from the model will be allowed based upon the rural provider's clinical judgement.

Patient participants who sign the informed consent form, receive the study intervention, then subsequently withdraw, or are withdrawn or discontinued from the study will not be replaced.

The following actions will be taken if a patient participant withdraws or fails to return the three month follow-up phone call:

- Before a patient participant is deemed lost to follow-up, the investigator or designee will make every effort to regain contact with the participant where possible, by completing up to 3 telephone calls. These contact attempts shall be documented in the participant's study file. Participants that do not agree to participate in the follow-up phone call will be asked to provide a reason for discontinuing participation.
- If the patient participant continues to be unreachable, they will be considered to have withdrawn from the study with a primary reason of lost to follow-up. The withdrawn date is the last day of attempted contact.

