9.0 INTEGRATED CARE MODEL INTERVENTION

9.1 Integrated Care Model

The integrated care model uses two tools to promote provider collaboration across rural and urban healthcare systems: 1) a care algorithm and 2) a referral checklist.

The care algorithm will be used by rural providers—primary care providers (PCPs) at UW Health Belleville clinic and rural diabetes and wound care specialists at SPH clinics—to guide integrated care for patients with diabetic foot ulcers (see Appendix). It supports rural providers, allowing most patients to be cared for locally and reserving urban specialty referral for those with limb-threatening disease. The algorithm triggers intensive medical management, especially for key gaps in vascular care. The rural providers will retain final clinical decision making autonomy; the algorithm is there as a general guide and clinical support tool with the ability to deviate from the algorithm when it is in the best interests of the patient. The model also supports rural patients by allowing both in-clinic and telemedicine urban specialty consultation. Rural patients and urban specialists jointly decide between in-person and telemedicine consultation for each visit.

The integrated care model's referral checklist will be used by rural schedulers who place referrals to urban specialists (see Appendix). It prompts schedulers to fax appropriate supporting documents (e.g., notes, labs, vascular testing results) with the referral request.

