10.2.2.3 Baseline Visit and Enrollment

Following informed consent, subject eligibility will be confirmed as follows:

A patient participant will be defined as "enrolled" in the study when they meet the following criteria:

- The patient participant has been consented by a research coordinator.
- The patient participant and a research coordinator have completed all screening documentation.
- The PI has verified that the patient participant meets all of the inclusion criteria.
- The PI has verified that patient participant meets none of the exclusion criteria.
- The patient participant completed a clinic visit with the participating rural provider, who considered recommendations outlined in the integrated care algorithm.

Following enrollment, the participant's medical record will be reviewed, and patient characteristic data will be abstracted. This will include sociodemographic data, comorbidities, medications, lab values, and ulcer characteristics. See Appendix for full list of variables.

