12.4.8 Process for Tracking Subject Consent and Authorization

Participants may withdraw consent by informing the PI in writing and specifying at that time whether they would like the study team to omit previously collected data pertaining to them from datasets and analysis. If this is not explicitly stated, the study team will use data collected about that study participant

from the time consent was originally signed up until the date the participant withdrew from the study. The research coordinator working with the clinic associated with the study participant who withdrew consent will be informed of their decision by the PI and asked to modify data sets and transcripts accordingly. It is the expectation that datasets will be amended due to participant withdrawal within one week of receiving written notice.

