13.2 Sample Size and Statistical Analysis

We have now finished enrolling active patients into the intervention. Our final number of active patients is 27. This is lower than our target enrollment of 45. Therefore, we re-calculated the number of historical controls needed to achieve adequate power for care processes. First we assume the probability of exposure among sampled control subjects is 0.6 and the correlation coefficient for exposure between matched cases and control subjects is 0.3. To detect an odds ratio of 0.26 versus the alternative of equal odds with 27 active patients and a matching sample of 5 historical controls per active patient (totaling 162 active and historical patients combined), and with a Type I error rate of 0.05, the power is 0.80706 (computed using PASS 2024, version 24.0.1).

When analyzing pilot data, descriptive statistics will be run on variables other than our primary and secondary outcomes. When analyzing our primary and secondary outcomes, we will stratify by clinic because they serve communities of differing socioeconomic status. Care processes will be modeled both dichotomously (all relevant completed vs. missing at least one) and continuously (as a percent of indicated care processes that occurred). In analyzing our primary outcome dichotomously, we will use a factorial experimental approach where the guideline-concordant and -discordant measures will be calculated. Additionally, due to the categorical nature of both our primary (dichotomously modeled care processes) and secondary (major and minor amputation) outcomes, we will build a multivariable Poisson regression model. When modeling guideline concordance care processes continuously, we use linear regression. In the primary analysis, we will require patients referred to a vascular or infectious disease specialist to be seen by that specialty, either in-person or via telemedicine, within 2 weeks per our algorithm. We will also conduct an intention-to-treat analysis where we include consults placed but not completed or delayed. Pre/post differences in completed referral rates, coupled with data on why a referral did not take place, will allow us to determine whether referral gaps would be best addressed by focusing on primary or specialty clinic processes.

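### Section 13.2 calls a relaxed scoring of consults 'intention-to-treat', and no described analysis includes a consented, eligible patient who fails the algorithm-considered enrollment condition

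*Combined protocol and SAP*

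**What the plan says.** Section 13.2 sets out two ways of handling specialist referrals. The first, used for the main comparison, sets a time limit counted in weeks: "we will require patients referred to a vascular or infectious disease specialist to be seen by that specialty, either in-person or via telemedicine, within 2". The second is described in one sentence: "We will also conduct an intention-to-treat analysis where we include consults placed but not completed or delayed". The section names no analysis set for either.

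Section 10.2.2.3 lists what makes a patient enrolled. Beyond consent, screening documents and verified eligibility, it requires this: "The patient participant completed a clinic visit with the participating rural provider, who considered recommendations outlined in the integrated care algorithm".

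Section 10.3.1 draws historical controls from medical records of the same clinics and providers, going back from 3 months before clinic activation. It applies the palliative-care, consent-capacity and insurance exclusions to them.

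Three other provisions bear on who stays in:

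- Section 9.1 allows departures from the tool: "the algorithm is there as a general guide and clinical support tool with the ability to deviate from the algorithm".
- Section 8.6 lets the PI withdraw a healthcare worker "for failure to consider use of the integrated care model with their patient participants". It adds that patients who withdraw after receiving the intervention, or who "are withdrawn or discontinued from the study will not be replaced".
- Section 12.4.8 covers a participant who withdraws without saying whether earlier data should be omitted: "If this is not explicitly stated, the study team will use data collected about that study participant", up to the withdrawal date.

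**The concern.** An intention-to-treat analysis is a rule about people: everyone who entered an arm is analysed in it, whatever care followed. The section 13.2 analysis is a rule about the endpoint. It scores the same patients more leniently and brings nobody back. A reader of the results would take the label as assurance that patients of non-using providers had not been selectively left out, and the analysis gives no such assurance.

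The assurance matters because of section 10.2.2.3. Membership of the active arm depends on an event after consent, and that event is tied to the provider's engagement with the intervention. The controls are a usual-care series with no corresponding condition. If a provider never considered the tool for a consented patient, that patient is not counted as enrolled, and the comparison loses a case in which the model failed to take hold. Section 14.3 says the pilot is meant to supply preliminary evidence of efficacy for a statewide trial, where providers not taking up the tool is an obvious way for the model to fail.

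**Working it through.** **1. The plan's own figure.** Section 13.2 gives power 0.80706 for 27 active patients, 5 matched controls each, control exposure probability 0.6, matched correlation 0.3, odds ratio 0.26 and Type I error 0.05. The Dupont formula for matched designs gives 0.803 two-sided, so the figure reproduces closely. This point does not show it to be wrong. The calculation takes 27 as the number analysed and does not address who was left out before that count.

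**2. Which patients are in a described analysis.**

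| Patient | Status under the documents |
|---|---|
| Provider considered the algorithm and followed it | Enrolled, analysed |
| Provider considered the algorithm and deviated | Enrolled, analysed (9.1, 10.2.2.3) |
| Enrolled, later withdrew | Data to withdrawal used by default (12.4.8); not replaced (8.6) |
| Enrolled, missed the 3-month call | Care processes and amputation still come from charts (10.2.3, Appendix 10) |
| Enrolled, provider later withdrawn by the PI | Effect on the patient not stated (8.6) |
| Consented and eligible, no completed visit or algorithm not considered | Not enrolled; in no described analysis |

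The section 13.2 intention-to-treat sentence moves no row of this table. It only changes whether a placed but unattended or late consult counts.

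**3. Timing of enrollment.** Section 10.2.2.3 makes considering the algorithm part of enrollment. Section 10.2.3.1 places the model activities after enrollment. Section 10.2.3.2 treats the model visit and enrollment as the same event. The boundary of the active arm therefore depends on which section is read.

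**4. Possible size.** Let k be the number of consented, eligible patients left out. The documents do not give k. Assume they had care like the controls. Inputs are 27 enrolled (13.2) and completion of 50% with the model and 20% without (Synopsis).

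Active-arm rate = (27 × 0.50 + k × 0.20) / (27 + k)

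- k = 0: 13.5/27 = 50.0%; difference 30.0 points
- k = 3: (13.5 + 0.6)/30 = 47.0%; difference 27.0 points
- k = 6: (13.5 + 1.2)/33 = 44.5%; difference 24.5 points

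Under this assumption any starting difference is multiplied by 27/(27 + k): 0.90 for k = 3 and 0.82 for k = 6. The section 13.2 inputs imply an active-arm probability of 0.6 × 0.26 / (1 + 0.6 × (0.26 − 1)) = 0.156/0.556 = 0.281, a gap of 31.9 points from 0.6. The same factors give 28.7 and 26.1 points, so the choice of rates hardly affects the proportional loss.

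**5. Effect on power, as illustration.** This uses an unmatched two-proportion test, two-sided 0.05, with 135 controls at 20%. Power = Φ[(d − 1.96 × SE₀)/SE₁], where d is the difference, SE₀ the pooled standard error and SE₁ the unpooled one.

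- k = 0: (0.300 − 1.96 × 0.0913)/0.1022 = 1.185; power 0.882
- k = 3: difference 27.0 points; power 0.845
- k = 6: (0.2455 − 1.96 × 0.0839)/0.0931 = 0.870; power 0.808

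**The case against.** The strongest reply is that the enrollment condition asks little. The provider must have considered the recommendations, not followed them, and deviation is allowed throughout the protocol. Section 11.2 says that healthcare worker retention does not depend on use of the model. A reader might infer that no analysis keeps non-adherent or withdrawn patients, or that the active arm is filtered on adherence. The documents do not support that, as the table shows.

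A reader might also infer that when the PI "may discontinue or withdraw a healthcare worker from the study at her discretion for failure to consider use of the integrated care model", that provider's patients drop out as well. Section 7.1 makes provider enrollment a condition for patient entry. Nothing says that patients already enrolled are then removed, and no such withdrawal is reported.

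Nor does the 2-week rule make the primary analysis a treated-only one. Its natural reading is a strict endpoint: a referred patient not seen in time fails the item and stays in the denominator.

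Three further objections carry weight:

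- The number left out may be zero. The telephone script in Appendix 5 links the enrollment payment to signing consent, which suggests that consent and enrollment may have coincided in practice.
- This is a non-randomized pre-post pilot, so there is no random allocation to preserve, and controls could not have met a condition about a tool that was not yet in use.
- Several care-process items are anchored to the baseline visit, so a patient without that visit is hard to score.

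These limit the likely size and show that the broader set needs a scoring rule. They do not rescue the label. Nor do they remove the asymmetry: that controls cannot face the condition is a reason not to impose it on one side only.

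**Conclusion.** The point holds in two parts. First, the section 13.2 analysis is misnamed: it relaxes consult scoring and sets no population rule. Second, section 10.2.2.3 makes active-arm membership depend on a post-consent condition that controls do not face, and any consented, eligible patient who fails it is in no described analysis. This can favour the active arm, but whether it did is unknown.

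The 27 to 24.5 point range rests on two assumptions: that 3 to 6 patients were left out, and that their care matched the controls'. If nobody was left out, the second part has no numerical effect and the remedy is a sentence saying so. The change should still be made before analysis, because a result labelled intention-to-treat would carry a reassurance that it does not provide.

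**What to change.** - Rename the section 13.2 analysis a referral-placed sensitivity analysis.
- Define the active-arm analysis set for the care-process and amputation comparisons as all consented patients meeting the section 8.1.2 criteria, whether or not the provider considered the algorithm or was later withdrawn. Use chart data as far as each patient's consent allows.
- State in advance how baseline-anchored items are scored for a consented patient with no completed visit.
- Report how many consented, eligible patients failed the section 10.2.2.3 condition, and keep the enrolled set as a sensitivity analysis.
- Reconcile section 10.2.2.3 with section 10.2.3.1 on whether model activities come before or after enrollment.

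The cost is small. Enrollment is closed, the section 11.2 logs already count patients who consented, and section 12.2 says that patient consent is combined with HIPAA authorization. At most a few charts need abstraction, and the estimated effect may be slightly smaller.

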13.3 Planned Interim Analysis

Not applicable.

13.4 Handling of Missing Data

Guidelines promulgated in the National Research Council report on handling of missing data will be followed.^{1,2}

14.0 RISK/BENEFIT ASSESSMENT

14.1 Known Potential Benefits to the Subjects

The potential benefits to patient participants associated with this study includes possible improvement of care for their diabetic foot ulcers. These improvements may extend to a reduction in the risk of major or minor amputation due to ulcers. Healthcare workers are not expected to benefit directly, though participation in the integrated care model may provide improved understanding of guideline concordant care of diabetic foot ulcers.

14.2 Known Potential Risks

There are no direct physical risks associated with the integrated care model. Patient participants' care will continue to be overseen by their primary care provider, who will retain final clinical decision making and will be allowed to deviate from the integrated care model should it be in the patient's best interest. To ensure there are no unforeseen negative consequences, the study team will track adverse events. The following is a list of adverse events that will be tracked by the study team:

- Hypoglycemia requiring hospitalization or an emergency room visit
- Adverse reaction to a smoking cessation product
- Muscle aches after starting or changing a statin
- Complication of a revascularization procedure
- Adverse reaction to a wound care product or dressing
- Adverse reaction to an antibiotic prescribed for an infection complicating the diabetic foot ulcer
- Hospitalization for a diabetic foot ulcer (occurs in 30% of patients with diabetic foot ulcers)
- Major (above-ankle) amputation (risk increases with ulcer severity but is 5% in the overall national cohort of patients with diabetic foot ulcers)
- Death
- Patient reported adverse events that the patient attributes to study participation

All serious, unanticipated adverse events, deaths (whether anticipated or not), and major amputations (whether anticipated or not) will be reported to the ICTR DMC within 14 days of the study team becoming aware of these events as well as the IRB. The baseline rate of major amputations among patients with diabetic foot ulcers is ~5% using national cohort data, although risk varies by ulcer severity.⁸ If the baseline rate in our pilot exceeds 15%, the study will be stopped and reviewed by the DMC and IRB for any necessary changes to the protocol. Particular attention will be paid to whether or not the major amputation caused by the integrated care model.

The primary risk to patient and healthcare worker participants is presented by a potential breach of confidentiality. These risks will be minimized by performing research activities in private spaces to the degree possible and complying with confidentiality procedures outlined above. Rural providers who participate may also face a risk to reputation. Again, this risk is minimized by protecting confidentiality.

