3.0	06/24/2024	
 1) Updated "[name]" with "[name]" (name and contact info) 2) Updated qualitative retention interview inclusion criteria 3) Updates and additions were made to the qualitative retention interview portion of the interview guide 	
 1) [name] has replaced [name] as research coordinator of the study. 2) We expanded our inclusion criteria and anticipated number of participants for the retention interviews so that we could include key informants from the clinic level, such as administrators. 3) We made some edits/additions after review of the first few retention interviews conducted with patient participants.
3.1	08/28/2024	Increased the number of healthcare worker (HCW) participants and patient participants for qualitative retention interviews by 1 each	A HCW that we'd like to interview was out on medical leave when we were recruiting; she has since returned to work and got back to us expressing interest in participating (and we have the funds to cover additional interviews). We are also increasing our maximum patient participants by one.
4.0	10/14/2024	Changed reimbursement method to Advarra, added patient information letter as a new retention strategy, added qualitative questions to see what patients thought about the new letter	UW policy is mandating switching to Advarra for study reimbursements as of 01/01/2025; initial qualitative interviews of patients suggested we should add a letter to serve as a reminder about the goals of the study and what to expect
5.0	02/06/2025	Updated ratio of active patients to historical controls & removed the date constraint for historical controls; removed [name]'s work phone number	
Per our statistician, with our final number of active patients, we need 135 historical controls for 80% power. We have exhausted our options within the date constraint initially included due to COVID. We think it's more important to be adequately powered and will include COVID as a limitation.
 
[name] will no longer have a dedicated UW number as of 2/28/25

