Statistical Methodology	Although this sample size is not powered to detect differences in major amputation, it does provide adequate power to find a difference in care processes proximal to major amputations. With a fixed sample size of 27 active patients, matched 1:5 pre/post with historical controls, alpha of 0.05, we are powered at >0.90 to detect an absolute increase of 30% (from 20% to 50% completion, measured dichotomously) in the group receiving integrated care.
Estimated Subject Duration	The duration of the study for each patient participant is approximately 3 months.
Estimated Enrollment Period & Study Duration	Study enrollment and follow-up will occur over 24 months with the total expected duration of the trial to be 36 months.

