8.5.2 Remuneration

Individual healthcare workers will not receive financial compensation for participating in the pilot. Rather, the clinics will be compensated \$4500 for their involvement. We doubt this nominal fee (compared to their overall operating budgets) will be enough to risk coercion from clinic managers to healthcare workers to participate. Patient participants who consent will be given \$100 upon enrollment and an additional \$100 upon completion of the 3-month follow-up. This has been in the form of cash for most of the duration of the study. However, starting in 2025, per UW-Madison policy, stipends for research participation must be paid using the Advarra payments system. Within this system, participants have the choice of a Visa card, direct deposit, or check. Enrollment will be completed in 2024 and payment for completion of the study is paid via mail. Since will be unable to work with the patient participants in person for this payment, and due to the nature of our patient participant demographics (majority elderly, several without email and/or limited access to internet/computers and/or transportation), we will be opting to send payment to all patient participants who complete the study in the form of a Visa card. Patient participants enrolled after 9/23/24 will be notified that although their enrollment payment is in the form of cash, they should expect payment for completion of the study in the form of a Visa card due to university policy changes. Patient remuneration may be revised as part of co-design adaptations.

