15.0 DATA AND SAFETY MONITORING

15.1 Unanticipated Problems

An unanticipated problem (UP), as defined by the DHHS Office for Human Research Protection (OHRP), is any incident, experience, or outcome that meets all of the following criteria:

- The incidence, experience, or outcome is unexpected given the research procedures described in protocol-related documents (e.g., the study protocol and informed consent documents) and the characteristics of the population being studied. An event may be considered unexpected if it exceeds the nature, severity, or frequency described in the study-related documents.
- The incidence, experience, or outcome is related or probably related to participation in the research study. “Probably related” means the incidence, experience, or outcome is more likely than not to be caused by the research study procedures.
- The occurrence of the incidence, experience, or outcome suggests that the research places subjects or others at a greater risk of harm (physical, psychological, economic, or social) than was previously known or recognized.

The investigator will report UPs to the reviewing IRB and ICTR DMC. The UP report will include the following information:

- Protocol identifying information: protocol title and number, PI's name, and the IRB project number;
- A detailed description of the event, incident, experience, or outcome;
- An explanation of the basis for determining that the event, incident, experience, or outcome represents an UP;
- A description of any changes to the protocol, informed consent documents, or other corrective actions that have been taken or are proposed in response to the UP.

For this study, UPs will include all major amputations and deaths, even though these are anticipated to some degree in this study population. Please see section 14.2 (Known Potential Risks) for further details. Study Stopping Rule will be a major amputation rate of 10% or more. Report UPs within the timeframe specified by the IRB of record and DMC.

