15.2 Safety Oversight

Safety oversight will be under the direction of a Data and Safety Monitoring Board (DSMB) composed of individuals with the appropriate expertise, including rural providers and specialists. Members of the DSMB should be independent from the study conduct and free of conflict of interest, or measures should be in place to minimize perceived conflict of interest. The DSMB will meet at least semiannually to assess safety and efficacy data on each arm of the study. The DSMB will operate under the rules of an approved charter that will be written and reviewed at the organizational meeting of the DSMB. At this time, each data element that the DSMB needs to assess will be clearly defined. The DSMB will provide its input to the PI and funder (NIDDK).

The ICTR DMC will provide an independent biostatistician to create reports of overall data analysis preparation for review by the DMC for bi-annual meetings.

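### The stopping threshold for major amputation is above 15% in section 14.2 but 10% or more in section 15.1, so 3 or 4 events among the 27 active patients meet one rule and not the other

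*Combined protocol and SAP*

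**What the plan says.** Section 14.2 (Known Potential Risks) cites a national rate of major amputation of about 5% and then sets a limit: "If the baseline rate in our pilot exceeds 15%, the study will be stopped and reviewed by the DMC and IRB". Section 15.1 (Unanticipated Problems) classes every major amputation as an unanticipated problem, tells the reader "Please see section 14.2 (Known Potential Risks) for further details", and in the next sentence sets another limit: "Study Stopping Rule will be a major amputation rate of 10% or more". Both sentences are current protocol text, not entries in the version log.

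Section 13.3 plans no interim analysis, so it supplies no look schedule or boundary that would choose between the two. Section 15.2 places oversight under a board whose charter is not among the documents; it says that at the board's organizational meeting "each data element that the DSMB needs to assess will be clearly defined".

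On the denominator, section 13.2 states: "We have now finished enrolling active patients into the intervention. Our final number of active patients is 27". The planned number was 45.

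**The concern.** Both sentences concern the same event, and both say that the study stops. The numbers differ, and so does the form of the inequality: strictly above 15% in one, at or above 10% in the other. A reader who starts at 15.1 and follows its cross-reference arrives at the other figure.

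The text does not support a two-tier scheme with review at the lower rate and stopping at the higher. The lower figure is the one labelled as the stopping rule, and 14.2 also says that the study stops.

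At stake is whether a given number of amputations obliges the study to stop. If 3 or 4 events occurred, the protocol cannot say whether a mandatory stop was triggered, or whether carrying on was a deviation under section 12.5. These two sentences are the only numerical safety boundaries in the protocol.

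A smaller wording point: 14.2 applies its limit to a *baseline* rate in the pilot. In context this must mean the rate observed in enrolled patients, since the paragraph goes on to ask whether the care model caused the amputation.

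**Working it through.** The plan gives no event count or operating characteristic for either rule, so there is no stated figure to reproduce. The check turns each percentage into a count and then asks how often the two rules would disagree.

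**Inputs**
- Rule A (section 15.1): stop if k/n ≥ 0.10.
- Rule B (section 14.2): stop if k/n > 0.15.
- n = 27 active patients (section 13.2). Neither rule names its denominator, so this is an assumption; other values are tried below.
- Risk p: the protocol's figure is about 5% (section 14.2), with no time horizon and said to vary with ulcer severity. I take p = 0.05, 0.10 and 0.15 as assumed 3-month risks.

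**Step 1: counts at n = 27**

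| Events k | k/27 | Rule A (≥10%) | Rule B (>15%) |
|---|---|---|---|
| 2 | 7.4% | no | no |
| 3 | 11.1% | stop | no |
| 4 | 14.8% | stop | no |
| 5 | 18.5% | stop | stop |

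The disputed counts are exactly 3 and 4.

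**Step 2: final-count probabilities, X ~ Binomial(27, p)**

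Rule A is met with probability P(X ≥ 3), Rule B with P(X ≥ 5), and the rules disagree with probability P(X ≥ 3) − P(X ≥ 5). For example, at p = 0.05:

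P(X ≥ 3) = 1 − [0.95²⁷ + 27(0.05)(0.95²⁶) + 351(0.05²)(0.95²⁵)] = 1 − [0.2503 + 0.3558 + 0.2434] = 0.1505.

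| Assumed p | P(Rule A met) | P(Rule B met) | P(3 or 4 events) |
|---|---|---|---|
| 0.05 | 0.1505 | 0.0100 | 0.1405 |
| 0.10 | 0.5154 | 0.1266 | 0.3889 |
| 0.15 | 0.7926 | 0.3813 | 0.4112 |

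**Step 3: other denominators**

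At n = 20 the disputed counts are 2 and 3 (10.0% and 15.0%, the latter not above 15%). At n = 25 the disputed count is 3 (12.0%). At the planned n = 45 they are 5 and 6 (11.1% and 13.3%), since Rule B needs 7 (15.6%). On a running denominator, 1 event is disputed when n is 7 to 10 (1/7 = 14.3%, 1/10 = 10.0%), and at least one count is disputed at every n from 14 to 45. Choosing 27 does not create the conflict.

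**Step 4: timing**

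Follow-up per patient is short: "The duration of the study for each patient participant is approximately 3 months" (section 3.1). The version 5.0 log entry of 02/06/2025, used here only for dating, already refers to a final count of active patients ("with our final number of active patients, we need 135 historical controls for 80% power"). Adding 3 months puts the last follow-up at about 05/06/2025 at the latest. Section 8.5.2 says "Enrollment will be completed in 2024"; on that basis it was due by about the end of March 2025. Actual last-contact dates are not given. The log entries for versions 3.0 to 6.0 list no change to the stopping rule, so the conflict probably also existed while patients were being enrolled; that is an inference.

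**The case against.** The strongest reply is that both sentences can be obeyed at once. Section 14.2 says what happens above 15%; it does not say that the study continues below that. Stopping at 10% breaches neither section, so the safer figure binds and the higher one is probably a number that was not updated. This is right as a reading for a board that applies both sentences, and it supports 10% as the default. It does not help someone who reads only 14.2 and carries on at 3 or 4 events.

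Second, there is little left to stop. Version 6.0 is dated 05/05/2025, so on the timing above follow-up was over, or within about a day of over, apart from late call-backs. This stands, and it confines the present effect mainly to DMC and IRB review, reporting and reuse of the text.

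Third, the probabilities apply each rule once, to the final count, whereas a safety rule operates as data accrue. One event in the first 6 patients (16.7%) would trip both rules. This also stands: the table in Step 2 does not describe how either rule would have behaved over time, and the values near 0.4 need a true risk two to three times the protocol's only figure. The conflict itself remains, because disputed counts also occur on running denominators.

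Fourth, oversight of individual events does not depend on either threshold. Each major amputation goes to the DMC within 14 days and to the IRB, and the unseen charter may settle the matter. These safeguards are real, but reporting an event does not say when the study must stop, and a charter that resolved the point would leave the protocol contradicting itself.

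**Conclusion.** The concern holds. It is an internal inconsistency in a participant-safety rule, and nothing in the documents resolves it. With 27 patients the rules part company at 3 and 4 events. The chance of ending there is 0.14 if the risk is 5%, rising to 0.39 and 0.41 at assumed risks of 10% and 15%; at 5%, the 10% rule is about 15 times as likely to be met as the 15% rule (0.1505/0.0100). These figures rest on a denominator of 27, a single look at the final count, and an assumed 3-month risk.

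It should be fixed, but it is not a reason to doubt the efficacy analysis. Closed enrolment and event-by-event reporting limit the harm to patients. What remains is review of any events that occurred, a clear statement of the governing rule in the results, and keeping the contradiction out of the statewide trial that this pilot is meant to prepare.

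**What to change.** - Put one threshold, worded identically, in sections 14.2 and 15.1. Define it as observed major amputations among enrolled patient participants, with the denominator stated, and drop the reference to a baseline rate.
- Have the sponsor and the DMC confirm which threshold governed during the trial. Events may already be known, so the choice should not be left open: apply the stricter rule, 3 or more of 27, unless the charter documents otherwise.
- State in the results report which rule was in force and how many major amputations occurred.
- Carry only the reconciled rule into the statewide protocol.

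The cost is a one-sentence amendment in each of two sections and a confirmation from the DMC. No new data are needed, and the analysis does not change.
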